#### **12.3.2 Parent and Legally Acceptable Representative Informed Consent**

Written informed consent will be obtained from the subject's parent/LAR before the subject participates in any study-related procedure. To provide consent for the subject's participation in the study, the subject's parent/LAR will read, assent to an understanding of, and sign an ICF or other locally applicable regulations and authorization form after having had an opportunity to discuss the forms with the Investigator. The parent/LAR will be made aware that the subject may withdraw from the study at any time and will receive a copy of the signed ICF. Subjects who reach the age of majority (i.e., 18 years in most jurisdictions) during the course of the study are required to be re-consented.

#### **12.3.3 Consent and Other Informational Documents Provided to Subjects**

The subject and/or parent/LAR must be given a copy of the signed informed consent and the original maintained in the designated location at the site.

#### **12.3.4 Consent Procedures and Documentation**

It is the Investigator or designee's responsibility to obtain written informed consent from the subject and/or parent/LAR after adequate explanation of the aims, methods, anticipated benefits, and potential hazards of the study. The subject and/or parent/LAR must be given ample time to decide about study participation and opportunity to inquire about details of the study. The IRB/EC-approved consent form must be personally signed and dated by the subject or parent/LAR with subject assent and by the person who conducted the informed-consent discussion. The

Investigator or appropriate site personnel must document the details of obtaining informed consent in the subject's study documents.

Records related to a study subject's participation will be maintained and processed according to local laws, and where applicable, the European Union General Data Protection Regulation (EU GDPR). The consent and study information documentation will include statements describing local and regional requirements concerning data privacy, and who to contact for questions.

#### **12.3.4.1 Remote Consent Procedures and Documentation**

In exceptional circumstances, and with the approval of the Medical Monitor, Investigators may obtain informed consent from the subject or parent/LAR when these individuals are unable to travel to the site where the Investigator is located due to extenuating circumstances (e.g., pandemic, natural disaster, or political upheaval). This is only permitted when a new consent is approved by the IRB/EC and the subject and/or parent/LAR need to be re-consented. The consent form may be sent to the subject or the subject's parent/LAR by facsimile or e-mail, and the consent interview may then be conducted by telephone when the subject or subject's parent/LAR can read the consent form during the discussion. After the consent discussion, the subject or the subject's caregiver can sign and date the consent form. Options for returning the document to the clinical Investigator may include facsimile, scanning the consent form and returning it through a secure e-mail account, or posting it to a secure internet address.

Alternatively, the subject or caregiver may bring the signed and dated consent form to his/her next visit to the clinical site, if restrictions on traveling to the clinical trial site are alleviated, or mail it to the clinical Investigator. The case history for each subject must document that informed consent was obtained prior to conducting any assessments at the visit the re-consent was conducted. The Investigator should have the subject and/or parent/LAR confirm verbally during the consent interview that the subject and/or parent/LAR has signed and dated the form. In addition, the person signing the consent form must receive a copy of the consent form.

### **13 PUBLICATION PLAN**

All publication rights are delineated in the Clinical Study Agreement and/or other separate agreements with the Investigator and/or Institution, as applicable.

### **14 CONFLICT OF INTEREST POLICY**

#### **14.1 Finance, Insurance, and Indemnity**

Arrangements for finance, insurance, and indemnity are delineated in the Clinical Study Agreement and/or other separate agreements with the Investigator and/or Institution, as applicable.

## 16 APPENDICES

### Appendix A Prohibited and Restricted Medicationsa

Subjects taking prohibited medications at study entry will not be eligible for the study.

Subjects who require current treatment with a prohibited medication will be withdrawn from the study.

Subjects who have previously taken a prohibited medication during the study will be withdrawn from the study unless:

- the prohibited medication has been discontinued AND
- withdrawal from the study presents an unacceptable medical risk to the subject

The justification to allow the subject to continue in the trial will be made by the Sponsor/Medical Monitor with medical input from the Investigator, and will be documented. If allowed to remain in the trial, this will be reported as a major protocol deviation and not a waiver.

The table below lists prohibitions and restrictions by medication class, including representative medications within class. A **prohibited** medication is not allowed. A **restricted** medication is allowed only under certain conditions.

Medication Class	Medication a	Prohibition/restrictions
Antiarrhythmic drugs	PROHIBITED 

• ajmaline

• amakalant, semantilide

• amiodarone

• bretylium

• disopyramide

• dofetilide

• dronedarone

• flecainide

• ibutilide

• procainamide

• propafenone

• quinidine

• sotalol, d-sotalol

	Prohibited at antecedent study entry and throughout the treatment period

Medication Class	Medication a	Prohibition/restrictions
Anticholinergics	PROHIBITED 
 
• Centrally acting anticholinergics 
 
◦ biperiden
 
◦ trihexiphenidyl
 
 
 
	Centrally acting anticholinergic medications are prohibited throughout the treatment period.
	RESTRICTED 
 
◦ benztropine
 
◦ oral diphenhydramine
 
	
 
◦ Benztropine (<math>\leq 6</math> mg/day) is allowed for movement disorders
 
◦ Oral diphenhydramine is allowed at <math>\leq 50</math> mg per day for acute extrapyramidal symptoms
 

	UNRESTRICTED 
 
• peripherally acting anticholinergics
 
• topical diphenhydramine
 
	Peripherally acting anticholinergic medications and topical diphenhydramine are allowed without restriction
Anticonvulsant and mood stabilizers	PROHIBITED 
 
• carbamazepine
 
• lamotrigine
 
• lithium
 
• oxcarbazepine
 
• phenytoin
 
• valproate
 
	Prohibited throughout the treatment period
Antidepressants	PROHIBITED 
 
• amitriptyline
 
• citalopram
 
• clomipramine
 
• desipramine
 
• desvenlafaxine
 
• doxepin
 
• duloxetine
 
• escitalopram
 
• esketamine
 
• fluvoxamine
 
• fluoxetine
 
• imipramine
 
• ketamine
 
• mianserin
 
• mirtazapine
 
	Prohibited throughout the treatment period

Medication Class	Medication a	Prohibition/restrictions
	
 
nefazadone
 
nortriptyline
 
sertraline
 
trazodone
 
trimipramine
 
venlafaxine
 
	
Antimanic agents	PROHIBITED 
 
lithium
 
valproate
 
	Prohibited throughout the treatment period
Antimicrobials, antifungals, and antimalarials	PROHIBITED 
 
clarithromycin
 
erythromycin
 
levofloxacin
 
moxifloxacin
 
pentamidine
 
roxithromycin
 
 RESTRICTED 
 
artenimol/piperaquine
 
azithromycin
 
bedaquiline
 
ciprofloxacin
 
fluconazole
 
gemifloxacin
 
norfloxacin
 
ofloxacin
 
telavancin
 
telithromycin
 
	Prohibited throughout the treatment period
Antipsychotics other than pimavanserin	PROHIBITED All in class	Prohibited throughout the treatment period
Anxiolytics	PROHIBITED 
 
chlordiazepoxide
 
diazepam
 
flurazepam
 
 RESTRICTED 
 
alprazolam
 
lorazepam
 
midazolam
 
	Prohibited throughout the treatment period 
 
Mild sedation is allowed exceptionally for ECGs and blood draws during the study (e.g., alprazolam at a pediatric-appropriate dose per age, and the lowest dose deemed necessary by the Investigator) just in
 

Medication Class	Medication a	Prohibition/restrictions
	
 
• oxazepam
 
• temazepam
 
• triazolam
 
	
cases when the subject's agitation/anxiety does not allow a safe and accurate measurement and the Investigator, with agreement from the caregiver, considers it safe and appropriate for the subject.
 
 
• Short- or medium-acting benzodiazepine may be used for acute anxiety
 
• May not be used within 12 hours prior to an assessment visit
 
• Lorazepam, in doses according to age, may be used as a rescue medication for a maximum of 7 consecutive days. Reassessment and discussion with Medical Monitor is required if needed beyond 7 days. 
 
○ If lorazepam is not available, another benzodiazepine from the restricted list may be used
 
 
 

Beta blockers	PROHIBITED 
 
• propranolol
 
	Prohibited throughout the treatment period
Centrally-acting alpha-agonist hypotensive agents	PROHIBITED 
 
• clonidine
 
	Prohibited throughout the treatment period
Centrally-acting alpha2A adrenergic receptor agonists	PROHIBITED 
 
• guanfacine
 
	Prohibited throughout the treatment period
Hypnotics and sleeping agents	PROHIBITED 
 
• eszopiclone
 
• zolpidem
 
• zopiclone
 
 RESTRICTED 
 
• melatonin
 
• ramelteon
 
• zaleplon
 
	
Prohibited throughout the treatment period
 
May not be used within 12 hours of a cognitive assessment, and efforts should be made to limit agents to lowest dose for the shortest time needed. 
 
○ Melatonin is allowed (≤5 mg/day) for insomnia
 
 

Non-stimulant ADHD medications	RESTRICTED 
 
• atomoxetine
 
	Allowed if stable throughout the antecedent study and the dose is expected to remain the same throughout the duration of the study.
Opioids	PROHIBITED 
 
• methadone
 
	Prohibited throughout the treatment period
Serotonin antagonists	PROHIBITED 
 
• cyproheptadine
 
	Prohibited throughout the treatment period

Medication Class	Medication a	Prohibition/restrictions
Stimulants and wake-promoting agents	RESTRICTED 

• amphetamine salts

• armodafinil

• lisdexamfetamine

• methylphenidate

• modafinil

	Allowed if stable throughout the antecedent study and the dose is expected to remain the same throughout the duration of the study.

Abbreviations: ADHD=attention-deficit hyperactivity disorder; ECG=electrocardiogram; QTcF=corrected QT interval using Fridericia's correction method; QRS=QRS interval on ECG; QT interval=QT interval on ECG

a Medications within each class include but are not limited to the examples listed in this table.

## Appendix B Prohibited and Restricted Concomitant Medications: Inhibitors and Inducers of Cytochrome P450 Enzyme 3A4

The information presented here is intended to provide guidance and does not constitute an exhaustive list of strong CYP 3A4 enzyme (CYP3A4) inhibitors and inducers. Any questions should be discussed with the Medical Monitor or appropriate designee.

Subjects who require current treatment with a prohibited medication will be withdrawn from the study.

Subjects who have previously taken a prohibited medication during the study will be withdrawn from the study unless:

- the prohibited medication has been discontinued AND
- withdrawal from the study presents an unacceptable medical risk to the subject

The justification to allow the subject to continue in the study will be made by the Sponsor/Medical Monitor with medical input from the Investigator, and will be documented. If allowed to remain in the study, this will be reported as a major protocol deviation and not a waiver.

The metabolism of pimavanserin is affected by strong CYP3A4 inhibitors, resulting in an increase in Cmax and AUC of approximately 3-fold.

Strong inhibitors of CYP3A4 are to be stopped at least 2 weeks or 5 half-lives prior to investigational product administration, whichever is longer. Strong inducers of CYP3A4 are to be stopped 30 days or 5 half-lives prior to investigational product administration, whichever is longer. Moderate inhibitors and inducers of CYP3A4 are allowed but should be used with caution.

STRONG INHIBITORS	grapefruit juice a boceprevir (Victrelis ® ) clarithromycin (Biaxin ® ) cobicistat (part of Stribild ® ) indinavir (Crixivan ® ) itraconazole (Sporanox ® ) ketoconazole (Nizoral ® ) lopinavir and ritonavir (Kaletra ® ) mibepradil (Posicor ® ) nefazodone (Serzone ® ) nelfinavir (Viracept ® ) posaconazole (Noxafil ® ) quinupristin (Synercid ® ) ritonavir (Norvir ® , part of Viekira Pak ™ )	MODERATE INHIBITORS	grapefruit juice a amprenavir (Agenerase ® ) aprepitant (Emend ® ) atazanavir (Reyataz ® ) ciprofloxacin (Cipro ® ) conivaptan (Vaprisol ® ) crizotinib cyclosporine darunavir/ritonavir (Prezista ® /Ritonavir) diltiazem dronedarone erythromycin (Erythrocin ® Lactobionate) fluconazole (Diflucan ® )
-------------------	--	---------------------	--

	
 
– combination treatments including ritonavir, such as: danoprevir and ritonavir elvitegravir and ritonavir indinavir and ritonavir lopinavir and ritonavir paritaprevir and ritonavir and ombitasvir (and/or dasabuvir) saquinavir and ritonavir tipranavir and ritonavir saquinavir (Invirase®) telaprevir (Incivek®) telithromycin (Ketek®) troleandomycin voriconazole (Vfend®)
 
		
 
fluvoxamine (Luvox®)
 
fosamprenavir (Lexiva®)
 
imatinib (Gleevec®)
 
isavuconazole
 
tofisopam
 
verapamil (Calan®)
 

STRONG INDUCERS	
 
apalutamide
 
avasimibe
 
carbamazepine (Tegretol®)
 
enzalutamide
 
ivosidenib
 
lumacaftor
 
mitotane
 
phenytoin (Dilantin®)
 
rifampin (Rifadin®, Rifadin® IV, Rimactane®)
 
St. John's Wort
 
	MODERATE INDUCERS	
 
bosentan (Tracleer®)
 
cenobamate
 
dabrafenib
 
efavirenz (Sustiva®)
 
etravirine (Intelence®)
 
lorlatinib
 
modafinil (Provigil®)
 
nafcillin (Unipen®, Nallpen®)
 
peoxidartinib
 
phenobarbital (Luminal®, Solfoton®)
 
primidone
 
sotorasib
 

a The effect of grapefruit juice varies widely among brands and is concentration-, dose-, and preparation-dependent. Studies have shown that it can be classified as a “strong CYP3A inhibitor” when a certain preparation was used (e.g., high dose, double strength) or as a “moderate CYP3A inhibitor” when another preparation was used (e.g., low dose, single strength). (FDA Drug Development and Drug Interactions <http://www.fda.gov/Drugs/DevelopmentApprovalProcess/DevelopmentResources/DrugInteractionsLabeling/ucm093664.htm#classInhibit>).

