### ***CNS, Psychiatric, and Illicit Drug Use Criteria***

2. Requires treatment with a medication prohibited by the protocol, including concomitant psychotropic drugs targeting irritability, including those used off-label (clonidine, guanfacine, and propranolol; lithium, valproate), medications that prolong the QT interval; and strong cytochrome P450 (CYP) 3A4 enzyme (CYP3A4) inhibitors and inducers (see [Appendix A](#) and [Appendix B](#))
3. Is at a significant risk of suicide, or is a danger to self or others, in the opinion of the Investigator based upon all available sources of information including C-SSRS (positive answer to suicidal ideation questions 4 or 5 [or positive answer to suicidal behavior questions at Baseline])
4. Is at risk of significant violent behavior to the extent that participation would pose an undue risk to other patients, caregivers, or others in the opinion of the Investigator
5. Has a positive urine drug test at Baseline. For study eligibility, the urine toxicology (drug) screen (UDS) must be negative for any substance for which the subject does not have a valid prescription.

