#### **4.8.2.1 Permitted, Restricted, and Prohibited Medications**

Prohibitions and restrictions for concomitant medications should be followed between the Baseline visit and Visit 6/EOT/ET as specified in [Appendix A](#) and [Appendix B](#). These appendices do not constitute an exhaustive list and any questions regarding prohibited and restricted medications should be discussed with the Medical Monitor or designee. The Investigator may prescribe appropriate medication to treat AEs.

Medications that can prolong QT interval are prohibited (or restricted) as specified in [Appendix A](#).

Permitted concomitant medications should remain at a stable dose throughout the treatment period.

If a subject is on a medication restricted by the protocol, the medication should be adjusted if it is determined by the Investigator to be clinically appropriate (e.g., if the subject's symptoms are not well-controlled or if the subject cannot tolerate the current medication) in consultation with the treating physician.

Subjects who require current treatment with a prohibited medication will be withdrawn from the study.

Subjects who have taken a prohibited medication during the study will be withdrawn from the study unless:

- the prohibited medication has been discontinued, AND
- withdrawal from the study presents an unacceptable medical risk to the subject

The justification to allow the subject who has taken a prohibited medication to continue in the trial will be made by the Sponsor/Medical Monitor, with medical input from the Investigator, and will be documented. If a subject is allowed to remain in the trial, this will be reported as a major protocol deviation and not a waiver.

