#### **4.8.3    Rescue Medications, Treatments, and Procedures**

Rescue medication, as determined by the Investigator, is permitted for a maximum of 7 consecutive days, provided it is consistent with the prohibitions and restrictions in [Appendix A](#) and [Appendix B](#).

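### Appendix A labels telithromycin as restricted, although Appendix B and exclusion 2 together bar it as a strong CYP3A4 inhibitor (minor safety-text error)

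*Protocol*

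**What the plan says.** Protocol Appendix A sorts concomitant drugs by class into prohibited, restricted and, in places, unrestricted. In the row for antimicrobials, antifungals and antimalarials, "telithromycin" is the last name in the restricted list; clarithromycin and erythromycin are in the separate prohibited list. Appendix A explains that a restricted "medication is allowed only under certain conditions".

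Protocol Appendix B covers CYP3A4 only. Its strong-inhibitor list contains the entry beginning "telithromycin (Ketek". It gives the pharmacological reason, "The metabolism of pimavanserin is affected by strong CYP3A4 inhibitors", and puts the rise in Cmax and AUC at approximately 3-fold. It also sets a washout: "Strong inhibitors of CYP3A4 are to be stopped at least 2 weeks or 5 half-lives prior to investigational product administration", taking the longer of the two. Moderate inhibitors and inducers are permitted with caution.

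Exclusion 2 (Section 4.2) counts "strong cytochrome P450 (CYP) 3A4 enzyme (CYP3A4) inhibitors and inducers" among the medications the protocol prohibits and refers to both appendices. Section 4.8.2.1 states "Prohibitions and restrictions for concomitant medications should be followed between the Baseline visit and Visit 6/EOT/ET as specified in" Appendices A and B. Section 4.8.3 allows rescue medication "provided it is consistent with the prohibitions and restrictions in" the same two appendices. None of these places says which appendix governs if they differ. Questions go to the Medical Monitor.

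**The concern.** The two appendices give different answers for one drug. Someone checking an antibiotic prescription would naturally open the antimicrobials row of Appendix A, and that row presents telithromycin as allowable under conditions. Appendix B and exclusion 2 put it in a barred class.

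Safety is at stake first. Section 1.5.1 says that pimavanserin prolongs the QT interval. It adds that adolescents taking it with other psychotropics showed dose-related QTc prolongation and a trend to higher exposure at lower age and weight. A strong inhibitor raises exposure further.

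Conduct is at stake second. If the drug is prohibited, Section 4.8.2.1 requires withdrawal of a subject who has taken it, unless it has been stopped and withdrawal would be an unacceptable medical risk; the exception is then reported as a major protocol deviation. If the drug is merely restricted, the same course may be compliant. Sites and monitors need one answer.

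**Working it through.** This is a comparison of lists. The plan gives no figure to reproduce.

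**Step 1: drugs named in both appendices.**

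| Drug | Appendix A | Appendix B | Consistent? |
|---|---|---|---|
| clarithromycin | prohibited | strong inhibitor | yes |
| nefazodone (spelled nefazadone in A) | prohibited | strong inhibitor | yes |
| carbamazepine | prohibited | strong inducer | yes |
| phenytoin | prohibited | strong inducer | yes |
| telithromycin | restricted | strong inhibitor | **no** |
| ciprofloxacin, fluconazole | restricted | moderate inhibitor | yes |
| modafinil | restricted | moderate inducer | yes |
| dronedarone, erythromycin, fluvoxamine | prohibited | moderate inhibitor | no, reverse direction |

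Five strong agents are shared. Four are prohibited in A and one, telithromycin, is restricted. It is the only case where A is more permissive than B. In the three reverse cases A is the stricter list.

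**Step 2: absence from A is not the problem.** Itraconazole, ketoconazole, posaconazole and voriconazole are strong inhibitors in B and are not named in A. That is no contradiction, because neither appendix claims to be exhaustive. Telithromycin differs because A gives it an affirmative label that points the other way.

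**Step 3: which rule operates.** Exclusion 2 and Sections 4.8.2, 4.8.2.1 and 4.8.3 each refer to A and B together. A restriction in one list does not waive a prohibition from the other, and a site can satisfy both by not giving the drug. So the drug should already be barred, and the A label is the text that needs correcting.

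**Step 4: size.** The only exposure figure is approximately 3-fold for strong inhibitors as a class. The documents give no figure specific to telithromycin and no usage rate. Scheduled ECGs fall at Weeks 0, 2, 6, 12, 20, 28, 36, 44 and 52, so the gaps are 2, 4, 6, 8, 8, 8, 8 and 8 weeks. A short antibiotic course after Week 12 could fall between two scheduled ECGs.

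**The case against.** The strongest reply is that nothing conflicts: the appendices are cumulative lists on different axes, and reading them together bars the drug. The reverse overlaps support this, since nobody would take B's permission for moderate inhibitors as overriding A's ban on erythromycin. This stands as an account of what the protocol requires. It does not rescue the label. Appendix A is not confined to QT drugs, and it already marks the other four shared strong CYP3A4 agents as prohibited, so telithromycin looks like a slip.

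A second reply is that the condition attached to the restricted antimicrobials is not visible in the text available. The Appendix A footnote defines QTcF and QRS, so an ECG condition may have been lost in extraction. That is fair, and its absence is not counted against the plan. A lost condition could reduce the risk, for example by requiring ECG limits or Medical Monitor approval. But by Appendix A's own definition a restricted drug remains allowable. The two labels are certain; what the full row tells a site is less so.

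A reader might also infer a specific overdose, for example by tripling 34 mg to 102 mg and calling that the worst case. The documents do not support it. The 3-fold figure is a class approximation, not an upper bound, and no population or variability is given with it. Estimates for a short course would need an assumed course length and immediate full inhibition. They would also carry dose proportionality seen in adolescents over to younger children.

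**Conclusion.** The point holds as a minor correction to safety text. One drug is mislabelled in Appendix A, and the label could mislead a site that checks only that row.

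Two stronger readings should be resisted. A reader might infer that the protocol permits a strong CYP3A4 inhibitor during treatment; it does not, because both appendices apply and exclusion 2 prohibits the class. A reader might also infer that results are at risk. No endpoint definition or analysis method changes, and every analysis uses all subjects who received at least one open-label dose (SAP Section 4).

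Rare use is a judgement, since the documents give no rate. The safeguards are real: subjects are told to consult the Investigator before taking any medication except in an emergency (Section 4.8.2), the Medical Monitor answers questions, ECGs are scheduled at every clinic visit (Section 6.4.3), and unscheduled visits allow any further safety evaluation (Section 6.7). They limit the risk but do not correct the row.

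**What to change.** Move telithromycin from restricted to prohibited in the antimicrobials row of Appendix A.

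As a supporting edit, add one sentence to Section 4.8.2.1 or to both appendices saying that where Appendices A and B differ, the stricter rule applies. This also settles dronedarone, erythromycin and fluvoxamine in favour of the Appendix A ban.

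The cost is one drug name moved, one sentence added and a notice to sites. The SAP needs no change.
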